8.2 Sample Size Determination

The sample size of 20 patients per phase has been determined using MIL-STD-105, a standard commonly used in the medical device industry to specify sample size and provide the basis for acceptance and rejection. We set an acceptable quality level (AQL) of 0.15 for the function of the new formulation hydrogel and using the C=0 sampling plan (Table 2), 100% testing of 80 devices with no failures would confirm that we meet our specified AQL.

If completed on 20 patients and assuming 4 days of use (on both legs), this equates to a minimum of 80 XT-3 devices to test the new formulation the same numbers would be required for the T3 device with current hydrogel formulation for statistical comparison.

Table 2: MIL-STD-105 Statistical Sampling Plan (C=0 Sampling Plan)

MIL-STD-1916																	
Verification Level	VII		VI		V		IV		III		II		I				
INDEX VALUE																	
AQL	.010	.015	.025	.040	.065	.10	.15	.25	.40	.65	1.0	1.5	2.5	4.0	6.5	10	
LOT SIZE		SAMPLE SIZE															
2 TO 5	*	*	*	*	*	*	*	*	*	*	*	*	5	3	2	2	
9 TO 15	*	*	*	*	*	*	*	*	*	*	13	8	5	3	2	2	
16 TO 25	*	*	*	*	*	*	*	*	*	20	13	8	5	3	3	2	
26 TO 50	*	*	*	*	*	*	*	*	32	20	13	8	5	5	5	3	
51 TO 90	*	*	*	*	*	*	80	50	32	20	13	8	7	6	5	4	
91 TO 150	*	*	*	*	*	125	80	50	32	20	13	12	11	7	6	5	
151 TO 280	*	*	*	*	200	125	80	50	32	20	20	15	13	10	7	6	
281 TO 500	*	*	*	315	200	125	80	50	48	47	29	21	16	11	9	7	
501 TO 1,200	*	800	500	315	200	125	80	75	73	47	34	27	19	15	11	8	
1,201 TO 3,200	1250	800	500	315	200	125	120	116	73	53	42	35	23	18	13	9	
3,201 TO 10,000	1250	800	500	315	200	192	189	116	86	68	50	38	29	22	15	9	
10,001 TO 35,000	1250	800	500	315	300	294	189	135	108	77	60	46	35	29	15	9	
35,001 TO 150,000	1250	800	500	400	4776	294	218	170	123	96	74	56	40	29	15	9	
150,001 TO 500,000	1250	800	750	715	476	345	270	200	156	119	90	64	40	29	15	9	
500,001 AND OVER	1250	1200	1112	715	536	435	303	244	189	143	102	64	40	29	15	9	

* Indicates entire Lot must be inspected 100%. **Note:** Acceptance number in all cases is zero.

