4.2 Follow-up and Daily Application of geko™ therapy (Days 1-9)

During daily review of the patient by a member of the healthcare team, a new geko™ device will be fitted bilaterally as per standard care. In addition, the following information will be collected each day or until the patient is able to mobilize independently:

- Length of time device worn for since fitting (hours)
- Adhesion to patient's leg (rate from very well to not at all)
- Use of additional fixation to keep the device in position
- Ease of re-application if removed
- Patient comfort (rate from very comfortable to extremely uncomfortable)
- Patient sleep post-fitting
- Patient's current mobility

Fit new geko™ device bilaterally for VTE prevention as per hospital standard care. Devices fitted will be as per allotted patient group and study phase and the following post-application information recorded:

- Ease with which device fitted (rate from very easy to impossible)

- Adhesion to patient's leg (rate from very well to not at all)
- Use of any additional fixation to keep the device in position.
- Patient comfort (rate from very comfortable to extremely uncomfortable)
- Device setting (1-11)
- Assess for any AEs

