7.4 Application of geko™ Device and Collection of Device Performance Data

Patients will receive treatment with either the geko™ T3 or XT-3 device as part of their standard care for VTE prevention as per hospital clinical protocol. During daily review of the patient by a member of the healthcare team, the following information will be collected for a maximum of 10 days or until the patient is able to mobilize independently:

- Length of time device worn for since fitting (hours)
- Adhesion to patient's leg (score from very well to not at all)
- Use of additional fixation to keep the device in position.
- Patient comfort
- Patient sleep post-fitting
- Patient's current mobility
- Ease with which device fitted (score from very easy to impossible)
- Device setting
- Assess for any AEs

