8.0 Statistical Analysis and Sample Size Determination

8.1 Statistical Analysis

The ability of the geko™ XT-3 device to adhere to skin will be numerically scored and compared to the geko™ T3 using a non-paired t-test for equivalence.

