-------------------------------	-------------------------------	-------------------------------	-------------------------------	-------------------------------	-------------------------------	-------------------------------	-------------------------------	-------------------------------	--------------------------------	--------------------------------

CASE REPORT FORM	BASELINE (DAY 0)			DATE (DD/MM/YYYY)				
STUDY SITE:	THE ROYAL STOKE UNIVERSITY HOSPITAL							
PRINCIPAL INVESTIGATOR:	[name]							
SITE NUMBER	0	2	5	PATIENT NUMBER	0		PATIENT INITIALS	

Has the patient experienced any Adverse Events since signing the Informed Consent?

Yes No

If yes, please comment below:

CRF completed by:

Print Name: _____ Signature: _____ Date: ____/____/_____

To be completed by Principal Investigator:

I am confident that the information supplied in this case record form is complete and accurate data.

Signature: _____ Date: ____/____/_____

Follow-up Day 1 (please note days 1-9 CRFs will be the same)

CASE REPORT FORM		FOLLOW-UP 1 (DAY 1)			DATE (DD/MM/YYYY)	
STUDY SITE: PRINCIPAL INVESTIGATOR:		THE ROYAL STOKE UNIVERSITY HOSPITAL [name]				
SITE NUMBER		0  2  5 	PATIENT NUMBER	0   	PATIENT INITIALS	

How many hours did the patient wear the geko™ device for?					_____ hours
How well did the geko™ device stick to the patient's leg?					
Very Well Remained attached 	Well Detached in small area 	Poorly Detached over large area 	Very Poorly Detached completely 	Not at all Would not stick at all 	

If any level of detachment has been indicated, please provide a comment below:

Did the patient need any additional fixation to keep the geko™ device in position?				
None 	Micropore Tape 	Adhesive Accessory 	OnPulse™ Knee Strap 	

If removed was the geko™ device easily re-applied?				
Yes 	No 	N/A 		

If no, please comment below:

Overall, how comfortable was the geko™ device for the patient to wear?				

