Very Comfortable 	Comfortable 	Uncomfortable 	Very Uncomfortable 	Extremely Uncomfortable 

If any discomfort has been indicated, please provide a comment below:

Did the patient sleep with the device on?		Yes 	No 
---	--	------------------------------	-----------------------------

DAY 1: Application of geko™ device

Current mobility - Is patient able to walk independently? (If YES is selected patient CANNOT continue in the study - please complete EXIT form)				Yes 	No 
Study Phase	geko™ Device Fitted		Lot Number	Expiry Date	
Phase 1		geko™ T3			
Phase 2		geko™ X-T3			

CASE REPORT FORM	FOLLOW-UP 1 (DAY 1)			DATE (DD/MM/YYYY)	/	/
STUDY SITE: THE ROYAL STOKE UNIVERSITY HOSPITAL	PRINCIPAL INVESTIGATOR: [name]					

SITE NUMBER

0	2	5
---	---	---

 PATIENT NUMBER

0		
---	--	--

 PATIENT INITIALS

--	--

How easy was it to apply the geko™ device to the patients leg?

Very Easy 	Easy 	Difficult 	Very Difficult 	Impossible 
---------------------------------------	----------------------------------	---------------------------------------	--	--

If there were any difficulties, please provide a comment below:

Once applied, how comfortable for the patient was the geko™ device?

Very Comfortable 	Comfortable 	Uncomfortable 	Very Uncomfortable 	Extremely Uncomfortable 
--	---	---	--	---

If any discomfort has been indicated, please provide a comment below:

Which setting was the geko™ device set to?

1 	2 	3 	4 	5 	6 	7 	8 	9 	10 	11 

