Appendix 4: Instructions for Use and Fitting Instructions geko™ X-T3

[figure not shown]
1 Location

[figure not shown]
2 Cleaning

[figure not shown]
3 Fitting

[figure not shown]
4 Turning On

[figure not shown]
5 Settings

Switching Off

7 Removing

The geko™ device is a neuromuscular electro-stimulation medical device and its intended use is:

- to increase blood circulation
- for the prevention of venousthrombosis
- for the prevention and treatment of oedema
- for the treatment of venous insufficiency and ischaemia

The device works by increasing blood circulation by stimulating the common peroneal nerve.

It is to be used on a single patient, in hospital, clinic and home environments. Apply to the affected leg or legs as advised by your Healthcare Professional (e.g. Nurse or Doctor). Patients should be trained in the positioning and operation of the device.

The geko device is intended for up to 24 hours continuous use, until it is no longer needed.

It may be removed for short periods of time when washing or having various tests (see warnings and precautions). Each device is single use and should be replaced every 24 hours, the device has an additional 6 hours run time.

Read this document fully before use and use only as instructed. Improper use of this device can be dangerous. Do not switch on unless correctly attached to the patient.

If assistance is required or to report difficulties, unexpected operation or events, contact the manufacturer. Visit the website for further advice and usage tips.

► Fitting Instructions

1 The marker line ►●◀ on the geko device should line up with the fibula head, a round lump below the knee on the lower leg. Ask your healthcare provider if you need help (e.g. nurse or doctor).

2 It should be applied to clean, dry skin. If there is too much hair in the area it should be removed using trimmers or clippers. Do not shave as this may cause irritation. Wash the skin in the area where the device will be fitted with mild soapy water, rinse, and dry thoroughly; do not apply any moisturizer.

3 Remove the film from the geko device and place the marker line ►●◀ over the fibula head (round lump). Attach the short end round the front of the leg and the longer end towards the back of the leg. The geko device should not be loose, peel off one end and tighten if needed. When correctly fitted, the + button will always be at the front of the leg.

4 To turn on, use a short press of the + button.

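### Section 8.2's own inputs give 160 devices per phase, not 80, and zero failures in 80 passes the C=0 plan without confirming an AQL of 0.15

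*Combined protocol and SAP*

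**What the plan says.** Section 8.2 sets an AQL of 0.15 for the function of the new hydrogel, takes 80 from Table 2 (acceptance number zero), and concludes that "100% testing of 80 devices with no failures would confirm that we meet our specified AQL". It links this to 20 patients as follows: "assuming 4 days of use (on both legs), this equates to a minimum of 80 XT-3 devices". The same number is asked of the T3 phase. No lot size, confidence level or definition of a failure is given.

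Other sections fix how many devices a patient-day uses. Section 4.2 says that at each daily review "a new geko™ device will be fitted bilaterally as per standard care". The instructions for use in Appendix 4 add: "Each device is single use and should be replaced every 24 hours". Section 7.4 collects data "for a maximum of 10 days or until the patient is able to mobilize independently", and the sample Day 1 form says of independent walking: "If YES is selected patient CANNOT continue in the study". That form asks "How well did the geko™ device stick to the patient's leg" once, with five answer categories and no left/right split.

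The planned comparison is separate. In section 8.1 adhesion is scored and "compared to the geko™ T3 using a non-paired t-test for equivalence". Section 8.4.1 adds descriptive summaries.

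**The concern.** There are two problems. The device count does not follow from the inputs stated beside it, and this paragraph is the only basis given for 20 patients per phase. The paragraph also treats passing an acceptance plan as confirming a quality level. A reader who later sees no failures could cite section 8.2 as showing that the new hydrogel fails in 0.15% of uses or fewer, which no result of this size can show. In addition, a claim of no failures cannot be judged until the plan says which adhesion categories are failures and which rating is used.

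**Working it through.** **Inputs.** From section 8.2: 20 patients per phase, 4 days, both legs, AQL 0.15, n = 80, acceptance number 0. From section 4.2 and Appendix 4: two new devices per patient-day. From section 7.4: at most 10 days. The AQL has no stated unit. I read it as percent, because the AQL row of Table 2 runs from .010 to 10 and so cannot be a proportion.

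**1. The plan's table figure.** The .15 column gives 80 for lots of 51 to 1,200, so 80 reproduces for those lots. It gives 120 for lots of 1,201 to 3,200 and rises to 303. Section 8.2 does not say which lot size it assumes.

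**2. The device count.** Devices = patients × days × legs = 20 × 4 × 2 = 160, not 80. Each way to reach 80 changes something stated:
- 20 × 4 = 80 counts patient-days, not devices.
- 20 × 2 × 2 = 80 uses 2 days.
- 10 × 4 × 2 = 80 uses 10 patients.

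**3. How often the plan passes.** With independent units and true failure rate p, P(no failures in 80) = (1 − p)^80.
- p = 0.15%: 0.9985^80 = 0.887
- p = 0.5%: 0.995^80 = 0.670
- p = 1%: 0.99^80 = 0.448
- p = 2%: 0.98^80 = 0.199

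A rate of 1%, more than six times the AQL, passes about 45% of the time. This result needs no choice of confidence level.

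**4. Upper limit after zero failures.** The one-sided 95% limit for 0/n is 1 − 0.05^(1/n).

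| n without failure | Source | Limit | Multiple of 0.15% |
|---|---|---|---|
| 80 | 20 × 4 patient-days | 3.7% | 24.5 |
| 160 | 20 × 4 × 2 devices | 1.9% | 12.4 |
| 200 | 20 × 10 patient-days | 1.5% | 9.9 |
| 400 | 20 × 10 × 2 devices | 0.75% | 5.0 |

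The last two rows need every patient to stay 10 days. A limit of 0.15% would need ln(0.05)/ln(1 − 0.0015) = 1,995.7, that is 1,996 failure-free units. Correcting 80 to 160 therefore does not rescue the word *confirm*, and neither does full follow-up.

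**5. Clustering.** Units come from only 20 patients, and the documents give no within-patient correlation. If it is assumed to lie between 0.1 and 0.5, a beta-binomial model solved for P(no failures) = 0.05 gives 4.2% to 7.0% for 80 patient-days and 2.5% to 5.4% for 160 devices. A design-effect approximation for the 80, n/(1 + 3 × ICC), gives effective sizes of 61.5 to 32 and limits of 4.8% to 8.9%. The size of the widening depends on the model, but both models widen the limit.

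**The case against.** The strongest reply is that nothing planned depends on this. Section 8.2 asks for a minimum, and 160 exceeds 80. No failure-count analysis is planned, and the t-test and summaries use the scores. All of that stands, and it limits the harm to the derivation of 20 and to the conclusion that section 8.2 licenses.

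A second reply is that, in acceptance sampling, meeting the AQL can simply mean passing the plan, and that the 95% level is mine. The level is indeed my choice. But the 45% pass probability at a true rate of 1% does not depend on it, and section 8.2 words its claim as being about the function of the formulation.

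A third reply is that testing the whole lot settles its quality. That is true only if the lot is exactly those 80 devices. For lots of 90, 150, 500 and 1,200, zero failures in 80 is still compatible at 95% with 1 (1.1%), 3 (2.0%), 16 (3.2%) and 42 (3.5%) failing devices. The objective in section 2.0 concerns routine clinical use, not 80 particular devices.

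A fourth is that 0.15 could be a proportion. At 15%, 0.85^80 is about 0.000002, so zero failures would exclude it easily. A scale that runs to 10 rules this reading out.

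Stronger readings are also tempting. A reader might infer that the study is short of devices, that the t-test is invalidated, or that 1,996 devices must be tested. The documents support none of these. The slip leaves more devices than the plan needs, the t-test does not use the failure count, and no endpoint asks for a rate of 0.15% to be demonstrated. A reader might also infer that the table was misread. It was not, for lots of 51 to 1,200; what is missing is the lot size.

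**Conclusion.** The point holds in this limited form. On section 8.2's inputs the count is 160 devices per phase, twice the stated figure, so the stated route to 20 patients does not follow: with the device as unit, 10 patients would supply 80. Zero failures in 80 meets the C=0 plan for lots of 51 to 1,200 but leaves a 95% upper limit of 3.7%, about 25 times the AQL. Even the largest yield, 0/400, leaves 0.75%, 5 times the AQL.

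These limits rest on reading the AQL as percent and on independent units, so they are optimistic. The clustered limits rest on assumed correlations and serve only to show the direction. The device arithmetic needs neither assumption, only that every patient completes 4 days of use; early exit would lower the count.

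**What to change.** Rewrite section 8.2, with no change in enrolment.

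(a) Name the unit. Give the count as 160 devices, or 80 patient-days, per phase if all 20 patients complete 4 days. State the lot size assumed. If the device is the unit, say openly that 20 per phase exceeds what the C=0 plan needs.

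(b) Replace the claim of confirming the AQL with: *zero failures would meet the C=0 acceptance plan*. Beside it, quote the one-sided 95% upper limit that zero failures would give: 3.7% for 0/80 patient-days on the current form, or 1.9% for 0/160 devices if left and right are recorded separately. Note that the limit assumes independence and is optimistic. If a patient-level limit is added, 1 − 0.05^(1/20) = 13.9% for 0/20, label it as the rate of patients with any failure.

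(c) Before data are seen, state which of the five adhesion categories count as a failure, and that the after-wear rating is used. Section 4.2 lists adhesion both after wear and after the new fitting, while the sample Day 1 form records it once.

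The cost is a few sentences. A left/right entry on the form is needed only if the device is the unit. No patients are added. The downside is that the stated claim becomes less favourable.

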3.2 Number of Participants

A total of 40 patients will be recruited, 20 into each phase of the study.

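### Section 8.2's inputs give 160 XT-3 devices rather than 80, nothing guarantees 80, and the plan does not say which 80 units its zero-failure rule covers

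*Combined protocol and SAP*

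**What the plan says.** Section 3.2 sets the size: "A total of 40 patients will be recruited, 20 into each phase of the study". Section 8.2 derives the 20 from a sampling table. It states a quality target, "We set an acceptable quality level (AQL) of 0.15 for the function of the new formulation hydrogel", and a criterion, "100% testing of 80 devices with no failures would confirm that we meet our specified AQL". The note under Table 2 confirms the zero: "Acceptance number in all cases is zero". To turn devices into patients, the section takes 20 patients with an assumed 4 days of use on both legs and concludes that "this equates to a minimum of 80 XT-3 devices to test the new formulation". It asks for the same number of T3 devices.

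Other sections govern how many devices a patient contributes:

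- Sections 4.1 and 4.2 fit a pair on Day 0 and a new pair on each of Days 1 to 9. Section 4.3 collects the last rating on Day 10.
- Section 7.4 has data collected "for a maximum of 10 days or until the patient is able to mobilize independently".
- The Day 1 form in Appendix 3, which serves for Days 1 to 9, asks about independent walking and instructs: "If YES is selected patient CANNOT continue in the study".
- Section 5.2 lets patients withdraw at any point.
- Each form has a single adhesion item on a five-point scale, with no left or right field.

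**The concern.** Two things in the Section 8.2 sentence do not fit. The inputs it names do not produce the figure it states. And a count built on an assumed duration of use is a minimum only if the design enforces that duration, which it does not. Section 3.1 describes patients confined to bed, but the inclusion criteria in Section 3.3.1 do not require immobility, and the baseline form records walking ability without acting on it. An exit on Day 1, after one wear, is therefore possible.

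The 80-device count is the only justification given for 20 patients per phase, and zero failures is the only explicit pass criterion in the plan. If a number other than 80 accrues, the plan is silent. With more than 80, it does not say whether all count or which 80 do; choosing after the ratings are known would make the result selectable. With fewer, it does not say what may be concluded. Nor does it say which of the five adhesion ratings is a failure, so the rule cannot be applied at any count.

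**Working it through.** **1. The plan's own figure.** Devices = patients × days × legs. With the inputs of Section 8.2, 20 × 4 × 2 = 160, twice the stated 80. Two other sets of inputs do give 80: 20 × 4 × 1 (one unit per patient-day) and 20 × 2 × 2 (2 days on both legs). The table look-up itself is right: in the .15 column of Table 2 the sample size is 80 for every lot size from 51 to 1,200.

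**2. Possible range per phase.**

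- Shortest stay, one wear each: 20 × 1 × 2 = 40 devices. Withdrawal before the first rating would lower this further.
- Longest stay, fittings on Days 0 to 9: 20 × 10 × 2 = 400 devices.
- With one adhesion rating per visit, the rated wear records are 20 × 1 = 20 to 20 × 10 = 200.

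Reaching 80 needs a mean of 80 / (20 × 2) = 2 wears per patient if the unit is a device on one leg, or 80 / 20 = 4 if it is a patient-day.

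**3. If every accrued device counted.** With independent devices and true failure rate p, the chance of no failures in n is (1 − p)^n. The documents give no value of p, so the rates below are assumptions. The unit of the AQL is not stated; I read 0.15 as a percentage. The last row is the one-sided 95% upper bound on the failure rate after zero failures, 1 − 0.05^(1/n).

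| | n = 40 | n = 80 | n = 160 | n = 400 |
|---|---|---|---|---|
| p = 0.15% | 94.2% | 88.7% | 78.6% | 54.9% |
| p = 1% | 66.9% | 44.8% | 20.0% | 1.8% |
| p = 2% | 44.6% | 19.9% | 4.0% | 0.03% |
| Upper bound after a pass | 7.2% | 3.7% | 1.9% | 0.75% |

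With patient-days as the unit and p = 1%, the chance is 82% at 20 records, 45% at 80 and 13% at 200.

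**4. Allowing for correlation within patients.** I used a beta-binomial model with m devices per patient and an assumed intraclass correlation r: a = p(1 − r)/r, b = (1 − p)(1 − r)/r, and chance of passing = [B(a, b + m) / B(a, b)]^20, where B is the beta function. At p = 1%:

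| | n = 40 | n = 80 | n = 160 | n = 400 |
|---|---|---|---|---|
| r = 0.1 | 68% | 50% | 30% | 11% |
| r = 0.3 | 71% | 58% | 46% | 32% |

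The dependence on n is weaker but remains.

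**5. If exactly 80 devices count.** With independent devices the chance is (1 − p)^80 whatever the length of stay, for example 44.8% at p = 1%. Extra wears then do no harm. A phase that yields fewer than 80 cannot meet the rule as stated.

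**The case against.** A reader might infer that the rule applies to however many devices accrue, so that the same gel passes or fails according to how soon patients walk. The documents do not support that as a finding:

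- Section 8.2 ties the rule to 80 devices, and Table 2 keeps 80 for lots of 51 to 1,200, a range that includes 400. A fixed 80 is at least as natural a reading, and on it the 160- and 400-device pass chances do not apply.
- 40 and 400 are extremes: all 20 patients leaving after one wear, or all 20 staying ten days. The documents give no distribution of stay, and for the population described in Section 3.1 universal walking on Day 1 is remote.
- No section makes the zero-failure rule the study's conclusion. Section 8.1 names an unpaired equivalence t-test against T3, and Section 8.4.1 describes summaries only.

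These points stand, and they limit the concern. They do not repair the sentence in Section 8.2. The arithmetic is wrong on either reading, and the design does not guarantee 80. The fixed-80 reading also leaves open which 80 count and what a shortfall means. Table 2 would have small lots (up to 50 at this AQL) inspected in full, but Section 8.2 does not define the trial's devices as a lot and words its criterion for 80. Nor need one look to the extremes: the plan's own 4-day assumption already gives 160 devices.

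**Conclusion.** The point holds in a limited form. On its own inputs Section 8.2 should give 160 devices; 80 fits only if the unit is a patient-day or the mean use is 2 days. Neither figure is a minimum: the possible range is about 40 to 400 devices, or about 20 to 200 rated wear records, per phase. The counted unit, the definition of failure, the choice of the 80 and the handling of a shortfall are all unspecified.

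The consequence depends on the reading. If all devices count, the pass chance at an assumed 1% failure rate falls from 45% at 80 to 20% at 160 and 1.8% at 400 under independence, and less steeply with within-patient correlation. If only 80 count, length of stay matters only through a shortfall. The failure rates, the correlations and the percentage reading of the AQL are assumptions. It does not follow that the trial's conclusion on XT-3 will turn on length of stay, because the plan does not say what part the zero-failure rule plays in that conclusion.

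**What to change.** In Section 8.2:

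1. Delete the claim that 80 is a minimum. State the count as 160 devices at 4 days on both legs, or as 80 patient-day ratings if that is the intended unit, and give the possible range. Calling 80 the expected number of devices would not do, because the stated inputs give 160.
2. Name the counted unit: the patient-day, as on the current form, or the device on one leg, with a left/right adhesion item added.
3. State which adhesion rating or ratings count as a failure.
4. Fix in advance which 80 units the rule covers, by an order that does not depend on outcome, and state that the rule is not assessable below 80.
5. Report the failure proportion over all rated units, with a confidence interval that allows for clustering by patient.

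This is mainly wording and needs no more patients. It does have costs. The stated figure becomes less firm. Units outside the fixed 80 inform the estimate but not the accept/reject rule. If leg-devices are taken in order of wear interval and all 20 patients contribute, 20 × 2 × 2 = 80 is reached after two wears each, so later wears would be left out of the rule. Counting by leg needs a small change to the case report form.

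### The lot-acceptance table in section 8.2 gives no basis for the equivalence t-test in section 8.1, although 8.2 calls its number required for that comparison

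*Combined protocol and SAP*

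**What the plan says.** Section 3.2 fixes the size: "A total of 40 patients will be recruited, 20 into each phase of the study". Section 8.2 gives the only rationale for it: "The sample size of 20 patients per phase has been determined using MIL-STD-105". The quality target is set for the new product alone: "We set an acceptable quality level (AQL) of 0.15 for the function of the new formulation hydrogel". The decision rule is that "100% testing of 80 devices with no failures would confirm that we meet our specified AQL", and the note under Table 2 adds: "Acceptance number in all cases is zero".

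Section 8.2 then reaches a minimum of 80 XT-3 devices by assuming 20 patients, 4 days of use and both legs. It carries the number over to the comparator: "the same numbers would be required for the T3 device with current hydrogel formulation for statistical comparison". Section 8.1 says what that comparison is: adhesion is scored numerically and XT-3 is compared with T3 "using a non-paired t-test for equivalence".

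The documents give no equivalence margin, SD, alpha, power or lot size.

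**The concern.** A lot-acceptance plan answers one question: how many items from a lot to inspect, and how many failures to allow, before accepting it. A two-group equivalence test asks whether the difference between two mean scores lies inside a margin. Its size depends on the margin, the SD, alpha and power. The first calculation contains none of these, so it cannot produce a number that the second requires.

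The stated objective is that the new hydrogel adheres at least as well as the current one, and section 8.2 is the only sample-size justification. A reader will take 20 per phase as having been chosen to support the equivalence conclusion. If the test then fails to show equivalence, or shows it against whatever margin is picked, the reader cannot judge what the study was able to show.

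The AQL claim has its own gap. Table 2 is entered by lot size as well as AQL, and the lot size is missing. The conclusion is also worded for the function of the formulation, whereas acceptance sampling speaks for the lots sampled.

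**Working it through.** **1. The plan's device count.** The inputs in 8.2 are 20 patients, 4 days and both legs. Section 4.2 has a new device fitted bilaterally each day. The count is 20 x 4 x 2 = **160**. The figure 80 follows from 20 x 4 (one device per patient-day) or from 10 patients x 4 x 2. Since 160 exceeds the minimum of 80, this is an error in the derivation and not a shortage of devices.

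**2. The table lookup.** Table 2, column AQL .15:

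| Lot size | Sample size |
|---|---|
| up to 50 | whole lot |
| 51 to 1,200 (five rows) | 80 |
| 1,201 to 3,200 | 120 |
| 3,201 to 35,000 (two rows) | 189 |
| 35,001 to 150,000 | 218 |
| 150,001 to 500,000 | 270 |
| above 500,000 | 303 |

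So 80 is the right entry for lots of 51 to 1,200 and for no others.

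**3. What zero failures in 80 shows.** I read AQL 0.15 as 0.15% nonconforming. This is an assumption: the unit is not stated, and the columns run from .010 to 10. Treating devices as independent:
- Upper one-sided 95% limit = 1 - 0.05^(1/80) = 3.7%.
- P(accept) at a true rate of 0.15% = 0.9985^80 = 0.89.
- P(accept) at a true rate of 1% = 0.99^80 = 0.45.

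These are properties of one product. No second group enters any of them.

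**4. What 20 v 20 delivers for the test in 8.1.** The assumptions are mine, because the documents give none: one score per patient, equal SDs and a true difference of 0. SE = SD x sqrt(2/20) = 0.316 SD, with 38 degrees of freedom. The CI half-width is t x SE. Power for two one-sided tests (TOST) is P(|d| < margin - t x s x sqrt(2/20)), integrated over the distribution of the sample SD s. Non-inferiority uses the non-central t.

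| | 5% per side | 2.5% per side |
|---|---|---|
| t(38) | 1.686 | 2.024 |
| Matching CI | 90% | 95% |
| CI half-width | 1.686 x 0.316 = 0.53 SD | 2.024 x 0.316 = 0.64 SD |
| Smallest equivalence margin, 80% power | 0.94 SD | 1.05 SD |
| Smallest one-sided non-inferiority margin, 80% power | 0.80 SD | 0.91 SD |

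At 5% per side, equivalence power with 20 per group is 3% for a margin of 0.5 SD, 40% for 0.7 SD, 51% for 0.75 SD and 86% for 1.0 SD.

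**5. The size the test would need.** No single number follows, because the margin and SD are missing. Under the same assumptions at 5% per side, patients per group for 80% / 90% power are:
- margin 0.5 SD: 70 / 88
- margin 0.75 SD: 32 / 40
- margin 1.0 SD: 18 / 23

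The required number depends strongly on an input that the acceptance table does not contain.

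**The case against.** **Twenty per group may be enough.** This stands. A reader might infer that the study is too small, or that it can support only a wide margin. The documents do not show either. Adhesion is rated on a five-category scale in Appendix 3, and no SD is given. If the patient-level SD were 0.5 category (an assumption), 0.94 SD would be 0.47 of a category. If it were 1.0, it would be 0.94 of a category. Averaging daily ratings could reduce the SD further. The fault is that the stated reason does not support the number, whether or not the number is adequate.

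**The lot size may not matter.** This stands in part. The entry is 80 for every lot from 51 to 1,200. The phrase about 100% testing of 80 devices could mean that the 80 are themselves the lot, which falls in the 51 to 90 row. The text does not say so, and on that reading the conclusion would cover only those 80 devices. A reader might infer that 80 comes from the wrong row, but the documents do not show that. Nor is 160 a ceiling: with up to 10 days of use, 20 x 10 x 2 = 400 devices are possible, more than the column's largest entry of 303.

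**The device may be the unit of analysis.** With 80 independent devices per group, power at a margin of 0.5 SD would be 87%. However, devices are clustered within patients. With 8 per patient and an assumed intraclass correlation of 0.1 to 0.8, 160 devices are worth 160/(1 + 7 x 0.1) = 94 down to 160/(1 + 7 x 0.8) = 24 independent ones. The acceptance table is silent on this as well.

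**The study is descriptive.** Section 8.4.1 does plan descriptive summaries, but sections 2.1.1 and 8.1 still promise an equivalence test, and 8.2 ties its number to a statistical comparison.

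**Conclusion.** The point holds. Section 8.2 claims a sample-size property that the design does not have: a one-product, zero-failure acceptance number is presented as required for a two-group equivalence test.

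What 20 per group delivers depends on alpha. At 5% per side it gives a 90% CI half-width of 0.53 SD and 80% power for a margin of 0.94 SD. At 2.5% per side the figures are 0.64 SD and 1.05 SD. They rest on the assumptions in step 4 of the working. Whether they are adequate cannot be settled until a margin and an SD are stated.

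The lot-size point is secondary and conditional. Zero failures in 80 supports acceptance of the sampled lot or lots if each lies between 51 and 1,200; it does not support a statement about the formulation in general. The count of 80 where the stated inputs give 160 is a plain arithmetic slip that leaves the stated minimum met.

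**What to change.** In section 8.2:

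1. Delete the clause that calls the number required for statistical comparison. State that 20 per phase was not derived from the test in 8.1. The sponsor should give the real basis for the number; the documents offer no other.
2. State what 20 per phase delivers at one chosen alpha, for one score per patient and a true difference of 0. At 5% per side: 90% CI half-width 0.53 SD and smallest equivalence margin with 80% power 0.94 SD. At 2.5% per side: 95% CI half-width 0.64 SD and margin 1.05 SD. If the aim is one-sided non-inferiority, the margins are 0.80 SD (5%) and 0.91 SD (2.5%). Do not pair an interval from one alpha with a margin from the other.
3. If the margin set in advance is smaller than the matching figure, report the result as an estimate with its CI.
4. If the AQL statement stays, give the lot size and limit the claim to the lots sampled. The CRF already records the lot number at each fitting. Drop the claim if the devices observed fall short of the matching row; do not enrol more patients to reach it.
5. Correct the device count to 20 x 4 x 2 = 160.

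The cost is wording, with no extra patients or procedures. The drawback for the sponsor is a less favourable justification, and the AQL claim may have to be dropped.
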